#### Regulatory statement

The study will be conducted according to the protocol and in compliance with Good Clinical Practice (GCP), with the Declaration of Helsinki, and with other applicable regulatory requirements.

# **LIST OF ABREVIATIONS**

Abbreviation	Definition
AE	Adverse Event
AUC	Area under the plasma concentration curve
BARS	Barnes Akathisia Rating Scale
BDI	Beck Depression Inventory
BID	Twice daily
BP	Blood Pressure
bpm	Beats per minute
CAG	Cytosine-Adenine-Guanine
CGI	Clinical Global Impression
C max	Maximum observed plasma concentration
CRA	Clinical Research Associate
CRO	Contract Research Organization
C-SSRS	Columbia-Suicide Severity Rating Scale
CT	Clinical Trial
DBP	Diastolic Blood Pressure
deuTBZ	Deutetrabenazine
DSMB	Data Safety Monitoring Board
ECG	Electrocardiogram
eCRF	Electronic Case Report Form
EMA	European Medicines Agency
ESS	Epworth Sleepiness Scale
FA	Functional Assessment
FDA	Food and Drug Administration
GCP	Good Clinical Practice
HD	Huntington's Disease
HPLC	High Performance Liquid Chromatography
HR	Heart Rate
HTT	Huntingtin gene
Htt	Huntingtin protein
IB	Investigator's Brochure
ICF	Informed Consent Form
ICH	International Conference of Harmonization

Abbreviation	Definition	
IMP	Investigational Medicinal Product	
IWRS	Interactive Web Response System	
MAO	Monoamine Oxidase	
MoCA	Montreal Cognitive Assessment	
PBA-s	Problem Behavior Assessment-short form	
PD	Pharmacodynamics	
PGI	Patient Global Impression	
PI	Principal Investigator	
PK	Pharmacokinetics	
PoC	Proof of Concept	
SAE	Serious Adverse Event	
SBP	Systolic Blood Pressure	
SmPC	Summary of Product Characteristics	
SOM3355	Bevantolol hydrochloride (racemate)	
SUSAR	Suspected Unexpected Serious Adverse Reaction	
TBZ	Tetrabenazine	
TEAE	Treatment Emergent Adverse Event	
TFC	Total Functional Capacity	
$T_{\text{max}}$	Time corresponding to occurrence of C max	
TMC	Total Maximal Chorea	
TMS	Total Motor Score	
UHDRS®	Unified Huntington's Disease Rating Scale	
US	United States	
VMAT2	Vesicular monoamine transporter type 2	

## 1. PROTOCOL SUMMARY

### 1.1. SYNOPSIS

Title	Phase IIb, randomized, double-blind, placebo-controlled study in parallel groups assessing the efficacy and safety of two doses of SOM3355 in patients suffering from Huntington's Disease with choreic movements.
Phase	Phase IIb.
Indication	Treatment of Huntington's Disease (HD) patients with choreic movements.
Rationale	Huntington's disease (HD) is an inherited progressive neurodegenerative disease. Chorea, an involuntary jerky movement that is purposeless and abrupt, is one of the most prominent symptoms in HD. No effective disease-modifying therapies exist for HD, and treatment is symptomatic relief. Chorea is treated by tetrabenazine (TBZ), approved in Europe and the United States (US), and the long-acting derivative deutetrabenazine (deuTBZ), approved in the US only. Both drugs are vesicular monoamine transporter type 2 (VMAT2) inhibitors depleting monoamines in presynaptic neurons. It is thought that the consequent modulation of dopamine signaling across neural synapses reduces the dyskinetic movements, such as chorea. The labels of both compounds carry a black-box warning by the Food and Drug Administration (FDA) and special warnings by the European Medicines Agency (EMA) since they can increase the risk of depression and suicidality in HD patients.
	SOM Biotech, using a computational virtual screening approach (SOM AI PRO) combined with in vitro screening methods, aimed to discover new potential treatments for HD that might offer clinical benefits over the current marketed HD treatments. Potential candidates were identified to be repositioned as VMAT2 inhibitors. One candidate named SOM3355 was bevantolol hydrochloride, developed and commercialized as an antihypertensive drug in Japan, China, and South Korea. In vitro , SOM3355 provided functional inhibition of the VMAT2 with similar potency to that of TBZ but different binding properties that may provide less risk of severe side effects. Relying on its VMAT2 inhibition activity, and the good tolerability shown in previous trials at doses from 100 to 600 mg/day administered once or twice daily (OD or BID), SOM Biotech is now developing SOM3355 for the treatment of the dyskinetic movement disorders related to HD.

	A first proof-of-concept (PoC) Phase IIa trial was conducted in 32 HD patients to test the efficacy and safety of SOM3355 100 and 200 mg BID doses compared to placebo. This provided confirmation of the expected effects of SOM3355 on the chorea symptoms measured by the Total Maximal Chorea (TMC) score, which significantly improved while patients were receiving 200 mg BID SOM3355 in comparison to placebo. SOM3355 was well-tolerated, with no concern about depression or suicidality risk, and the most frequent treatment emergent adverse events, all mild or moderate, being bradycardia, hypotension, insomnia, and falls, which were expected and explained by the known effects of the drug.  Following the results of the first PoC and the PK-PD assessment indicating that higher doses may be more efficacious, this Phase IIb study will be conducted.
Objectives	The primary objective of the study is to assess the efficacy of two doses of SOM3355 (400 mg/day and 600 mg/day taken twice daily [BID] over at least 8 weeks at maintenance dose) compared to placebo to reduce chorea in HD patients measured by the change in TMC score (primary efficacy endpoint). Secondary objectives of the study are:  To evaluate the safety and tolerability of two doses of SOM3355 (400 mg/day and 600 mg/day taken) compared with placebo in HD patients, with particular attention to depression and suicidality and to the cardiovascular hemodynamic parameters.
	And to evaluate the efficacy of the two doses of SOM3355 (400 mg/day and 600 mg/day taken BID) compared with placebo on:  the change of Clinical Global Impression (CGI-C), the change of Patient Global Impression (PGI-C), the percentage of responders based on the improvement ≥2 in TMC score, the percentage of change of TMC score.  A pharmacokinetic (PK) sub-study in a subset of 24 patients will allow to determine the PK profile of the two doses of SOM3355 (200 mg and 300 mg given twice per day) at steady state and to model PK-PD assessments of hemodynamic and cardiac parameters.
Study design	This is an international, multicenter, double-blind, randomized, placebo-controlled, parallel-group Phase IIb study assessing two doses of SOM3355 (400 or 600 mg/day), taken as 200 mg BID or 300 mg BID, in patients presenting choreic symptoms related to HD.

Patients who meet all of the eligibility criteria will be randomized at the inclusion visit (Visit 1) to one of 3 treatment arms to receive either SOM3355 400 mg/day, SOM3355 600 mg/day, or placebo, all given BID. Dosing will start with an up titration in the first 3 weeks and will be maintained at a fixed dose for 7 weeks. After 10 weeks, patients will down titrate to 1 capsule a day of study drug for 1 week, followed by 1 capsule a day of placebo to assess the effect of drug interruption. Ambulatory patients will be recruited by reference centers for HD in collaboration with patient advocacy groups and the European HD network. A sub-study will characterize the PK profile of the 2 doses (400 mg/day or 600 mg/day) given twice daily for at least one week in a subset of patients (n = 24) who consent to be hospitalized for 24 hours for blood sampling and cardiac and hemodynamic assessments. Sample size A total of 129 patients (43 in each arm, accounting for a drop-out rate of 10%) will be randomized (1:1:1). Eligibility criteria to participate in this study are: Inclusion criteria 1. Males or females  $\geq 21$  years old. 2. Patients with a diagnosis of Huntington's Disease determined by a movement disorders expert and confirmed by a number of HTT gene cytosine-adenosine-guanine (CAG) repeats  $\geq$ 36. 3. UHDRS® Total maximal chorea (TMC) score ≥10. 4. UHDRS® Total Functional Capacity (TFC) ≥7 (corresponding to mildly to moderately impaired patients). 5. Able to walk independently or with minimal assistance. 6. Females of child-bearing potential must use a medically accepted effective method of birth control, agree to continue this method for the duration of the study and for at least 1 month following the last dose of study drug, and be negative to serum pregnancy test performed at the screening visit (Refer to section 5.4 for complete advice on contraception requirements of this study). Female patients should not be breastfeeding. 7. In the opinion of the Investigator, the patient must have adequate support to comply with the entire study requirements as described in this protocol (e.g. transportation to and from the trial site, self-rating scales, drug compliance, scheduled visits, etc.).

	8. Able and willing to provide written informed consent prior to any study-related procedure being performed at the screening visit.
Exclusion criteria	Patients are excluded from the study if any of the following criteria apply:  1. Onset of HD symptoms prior to age of 21 years, corresponding to juvenile forms of HD.
	2. HD patients presenting rigid akinesia.
	3. Use of other vesicular monoamine transporter type 2 (VMAT2) inhibitors such as tetrabenazine, deutetrabenazine, or valbenazine within 3 months before enrollment, and at any time during the study period; and use of other antichoreic treatment such as any neuroleptic within 2 months or amantadine, memantine, riluzole within 1 month before enrollment and along the study.
	4. Patients who experienced severe depression or suicide attempt in the last 5 years.
	5. Severe untreated or under-treated psychiatric illness such as active suicidal ideation or behavior (BDI-21 item #9 >0 and active suicidal ideation in C-SSRS) or depression at screening and/or initiation visit (BDI-21 items total score >30); although patients taking authorized antidepressant therapy at a stable dose for at least 2 months and stabilized can be enrolled.
	6. Patients with a history of, or current, hypotension (SBP <110 mmHg), bradycardia (HR <50 bpm), or orthostatic hypotension as defined by the European Society of Hypertension (reduction in SBP ≥20 mmHg or in DBP ≥10 mmHg).
	7. Patients with hypertension already treated with more than 2 antihypertensive drugs.
	8. Other active clinically significant illness, including unstable cardiovascular disease, angina pectoris, congestive heart failure, pulmonary hypertension, peripheral arterial disease, history of pheochromocytoma, asthma, COPD, diabetic ketoacidosis or metabolic acidosis, or neoplastic pathology, which could interfere with the study conduct, or counter-indicate the study treatment, or to place the patient at risk during the trial, or compromise their study participation.
	9. Any significant serious abnormality in the electrocardiogram (ECG), e.g. recent myocardial infarction, significant sinus bradycardia (<50 bpm), atrioventricular block (grades I to III with PR >240msec), sinoatrial block, atrial sinus disease or prolonged QTc interval at screening (ECG

Bazett's corrected QT interval (QT  $/\sqrt{[HR/60]}$  >450 msec for males or >470 msec for females), or a known history of long QTc syndrome.

- 10. Patients with severe hepatic impairment, or with severe renal impairment, or with any other significant abnormality in the physical examination or clinical laboratory results that, in the Investigator's opinion, would not be compatible with study participation or represent a risk for the patient while in the study.
- 11. Females who are pregnant or lactating, or who intend to become pregnant during the study period.
- 12. Patients with allergy under desensitization, with known psoriasis, or a known allergy / hypersensitivity to any ingredients of the trial medication or placebo.
- 13. History of alcohol or substance abuse in the previous 12 months.
- 14. Patients participating in any other study, and the use of any investigational therapy, within 1 month prior to entry in this study.

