(P=0.0224), which was confirmed in ratings of CGI-C and PGI-C. In the other outcome measures of the UHDRS®, no statistical differences were found between SOM3355 and placebo. SOM3355 was well tolerated with only mild or moderate AEs, and with no implications for depression or suicidality risk. The most frequent AEs during SOM3355 administration, all mild or moderate, could be explained by the known effects of the drug such as insomnia, and bradycardia or hypotension that are both related to the β1-blocking effects of bevantolol. Mild elevations in plasma prolactin levels were recorded with SOM3355 (P<0.005), probably reflecting the inhibitory effect on the dopamine pathway, consistent with the profile of VMAT2 inhibition. This study confirmed that SOM3355 reduces chorea in patients with HD and has a good safety profile.

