#### 2.2. RISK / BENEFIT ASSESSMENT

#### 2.2.1. Known Potential Risks

Bevantolol is a cardio selective  $\beta$ 1-blocker that is shown to selectively block the positive chronotropic and inotropic action of isoproterenol and is essentially devoid of intrinsic sympathomimetic activity (ISA). It has a mild chronotropic effect at rest and reduces exercise-induced tachycardia and pressor responses. The  $\beta$ 1-blocking effects are almost at the same level as that of metoprolol ( $\beta$ 1-selective blocker), while being slightly weaker than the effect of propranolol ( $\beta$ 1-nonselective blocker).

The safety profile of SOM3355 (bevantolol) in healthy subjects and patients with cardiovascular diseases is well characterized and demonstrated to be safe and tolerable up to 600 mg/day. Therefore, there is no specific reason to suspect that the administration of this compound in non-hypertensive patients can induce clinically relevant complications and in the first trial conducted in HD patients it was well tolerated at doses up to 400 mg/day (see Investigator's Brochure § 7.2). The most frequent AEs during SOM3355 administration in the first Phase 2a study in HD patients were all mild or moderate, did not induce treatment withdrawal, and could be explained by the known effects of the drug such as insomnia, and also bradycardia and hypotension (which are both related to the  $\beta$ 1-blocking effects of bevantolol).

Safety assessments will include monitoring of HR and BP at each visit (measured according to standardized conditions, first in the sitting position and then in the supine and standing positions to detect orthostatic hypotension), and ECG performed at key visits will be assessed with central reading.

Moreover, a wide variety of neuropsychiatric symptoms occur in HD, including, depression, anxiety, irritability, obsessive compulsive behavior and psychosis. Depression is the most common condition

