#### 2.2.3. Assessment of Potential Risks and Benefits

Patients could benefit from treatment with SOM3355, which is known to reduce chorea symptoms as shown in the previous Phase 2a study, and it will be assessed as the primary endpoint.

SOM3355 is a well-known drug which has proven its good safety profile since more than 25 years of use as hypertensive drug. It has no warning regarding neuropsychiatric side effects and it was also well tolerated in the previous trial in HD patients, with no worsening of depression or suicidality although the sample was very limited.

Safety will be carefully monitored along the trial, particularly the risk of depression and suicidality will be assessed at each visit by the physician through specific scales (Beck Depression Inventory and Columbia-SSRS). Patients with known depression should be treated and stabilized with antidepressant therapy. Patients with severe untreated or under-treated depression at screening, or presenting a risk of suicide (item on suicidality >0 in BDI scale) are excluded from this study, and if the risk of suicide arises during the trial the patient should be immediately withdrawn from the study.

The known effect of bevantolol as beta blocker may induce potential side effects such bradycardia or orthostatic hypotension. Patients with a history of, or current, hypotension or bradycardia (HR <50 bpm) at the screening will be excluded from the study. Hemodynamic parameters (HR and BP) will be carefully monitored during the study as well as the recording of ECG to assess any abnormality. Severe permanent bradycardia will be excluded.

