## 7.4. SAFETY REPORTING

## 7.4.1. Definitions

# 7.4.1.1. Adverse Event (AE)

The term Adverse Event covers any sign, symptom, syndrome, or illness which appears or worsens in a patient during the observation period in the clinical study, and which may impair the patient's well-being.

The term also covers laboratory findings or results of other diagnostic procedures which are considered to be clinically relevant (e.g. requiring unscheduled diagnostic procedures or treatment measures, or result in withdrawal from the study).

An AE may be:

- A new illness.
- The worsening of a sign, or symptom of the condition under treatment, or of a concomitant illness. Associated symptoms of Huntington's Disease (such as akathisia or dystonia) should not be considered as AEs except if they increase in terms of intensity and/or frequency.
- A known effect of the study medication (as listed in the SmPC).
- A combination of two or more of these factors.

No causal relationship with the study medication or with the clinical study itself is implied by the use of the term "Adverse Event."

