## 7.4.2. Procedures for recording, analyzing and reporting AEs

# 7.4.2.1. Monitoring and recording of AEs

At each visit, occurrence of AEs will be assessed by verbally asking the patients if they have had any problems or symptoms since their last visit.

For each AE, regardless of the suspected causal relationship to study drug, the Investigator has to report on the AE page(s) of the eCRF the relevant information of the AE including the nature, the anteriority (emergent or not), the timing of event occurrence and resolution, the frequency (intermittent or continuous), the severity (mild, moderate, severe), the relationship with the study drug, and actions taken to treat the adverse experience. The Investigator has also to pursue and obtain adequate information in order to determine the outcome of the AE and also to assess the seriousness, i.e. whether it meets the criteria for classification as a SAE requiring immediate notification to the Sponsor.

Whenever possible, a unifying diagnosis should be recorded in the eCRF as the AE rather than individual signs or symptoms. Similarly, the unifying diagnosis should be recorded as the AE rather than the abnormal laboratory result (i.e. "anemia" instead of "low hemoglobin"). If the AE is a worsening of a past medical condition, the AE should clearly indicate that the past medical condition has worsened using words such as "worsening," "aggravated," or "exacerbation."

AEs will be coded according to the Medical Dictionary for Regulatory Activity (MedDRA current version). AEs will be individually listed per patient number, presenting System Organ Class (SOC), preferred term, emergence, description, date and time of onset, date and time of last study drug administration before AE, duration, time from onset since last study drug administration, frequency, severity and seriousness, relationship to study drug, the required action taken (corrective treatment, hospitalization), and outcome if any.

All AEs (including SAEs) must be followed until satisfactory resolution or stabilization.

Any AE and any measure taken and follow-up result must be recorded in the patient's eCRF, as well as in the patient's source document. Follow-up laboratory results should be filed with the patient's source documentation.

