#### 4.10.1 Adverse events

Adverse events (AEs) will be presented by MedDRA System Organ Class (SOC) and Primary Term (PT). Coding of verbatim terms will be performed by Ergomed and all relevant codes are stored in the database and it will be approved by the Sponsor before database lock (cf. DMP).

Only treatment-emergent adverse events (TEAE) will be analysed, i.e. all new and worsened pre-existing adverse events occurring on or after the initiation of IMP. It is assumed that for each change in intensity, relationship, or seriousness of an AE a new entry of the AE was recorded in the data capture database; hence such cases will be analysed like different phases of the same AE.

An overall summary of TEAEs will be presented including both the number and percentage of patients with a given AE category and the number of events:

- All TEAEs
- Serious TEAEs (STEAEs)
- Treatment-related TEAEs
- Treatment-related Serious TEAEs
- Severe TEAEs
- TEAEs leading to study drug discontinuation
- Fatal TEAEs

A descriptive analysis will be performed. Global incidences of primary system organ classes (SOC) and preferred terms (PT) will be calculated for:

- All TEAEs irrespective of the causality assessment
- Serious TEAEs (STEAEs)
- TEAEs by relationship
- STEAEs related to study drug
- TEAEs by maximum severity
- TEAEs leading to discontinuation
- Fatal TEAEs

Statistical Analysis Plan	Version 1.0		Page 26 of 37
Sponsor	SOM Biotech	Protocol No	SOMCT03

These tables will be presented by treatment group and also include summary lines for all SOCs and the occurrence of any event of the specified type. SOC terms will be presented according to the Internationally Agreed Sorting Order (MedDRA).

Multiple counts within a PT or SOC (repeated or different included terms or changes in descriptors) will be counted only once for the calculation of incidences. In addition to the incidences, the number of reported AEs (within a PT or SOC) will be included in the summaries.

Detailed listings of all fatal and other serious events will be provided (for section 14.3.2). All adverse events (i.e. TEAEs as well as non-treatment emergent events) will be listed in section 16.2.

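### The synopsis names falls as a frequent, drug-explained adverse event, but the risk sections omit them and the recording and tabulation rules may undercount them

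*Protocol*

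**What the plan says.** **Risk text**

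- Protocol 1.1 (Synopsis, rationale) lists the most frequent events of the Phase IIa trial as "being bradycardia, hypotension, insomnia, and falls, which were expected and explained by the known effects of the drug". It gives no counts by arm.
- Protocol 2.1.6.1, on the same trial, says the most frequent events "could be explained by the known effects of the drug such as insomnia, and bradycardia or hypotension that are both related to the β1-blocking effects".
- Protocol 2.2.1 says they "could be explained by the known effects of the drug such as insomnia, and also bradycardia and hypotension".
- Protocol 2.2.3 says that beta blockade "may induce potential side effects such bradycardia or orthostatic hypotension".
- Protocol 2.1.1 ties falls to chorea and cites them as a strong predictor of nursing home admission.

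**Recording**

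- Protocol 7.4.2.1 elicits events with an open verbal question at each visit and adds: "Whenever possible, a unifying diagnosis should be recorded in the eCRF as the AE rather than individual signs or symptoms". The worked example that follows is a laboratory value.
- Protocol 7.4.1.1 says that associated symptoms of HD, with akathisia and dystonia as examples, "should not be considered as AEs except if they increase in terms of intensity and/or frequency".

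**Tabulation**

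- SAP 4.10.1: "Global incidences of primary system organ classes (SOC) and preferred terms (PT) will be calculated for" a set of categories that includes all treatment-emergent events, whatever their judged causality. Tables are by treatment group and show patients and events. No individual event is named and no terms are grouped.

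**The concern.** The sponsor's own summary treats falls as a frequent event explained by the drug. A reader who goes only to the risk sections would not learn this. The trial also tests 600 mg/day, whereas 2.2.1 describes HD experience up to 400 mg/day. The population is already prone to falls, and the drug can lower blood pressure.

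The comparison of falls between arms depends on falls being entered as falls. If the rules allow some to be entered under a blood pressure diagnosis, or left out as part of the disease, the preferred-term row is not the number of patients who fell. At stake is how reliable the safety comparison is for one named event. The primary analysis is not affected.

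**Working it through.** **1. The four risk passages side by side**

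| Protocol section | Events named | Falls? |
|---|---|---|
| 1.1 Synopsis | bradycardia, hypotension, insomnia, falls | yes |
| 2.1.6.1 | insomnia, bradycardia, hypotension | no |
| 2.2.1 | insomnia, bradycardia, hypotension | no |
| 2.2.3 | bradycardia, orthostatic hypotension | no |

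The first three describe frequent events in the same trial. One of the four events in the synopsis is absent from the others.

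**2. How a fall could miss the fall row**

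- *Unifying diagnosis (7.4.2.1).* A fall after a drop in blood pressure can be entered as hypotension alone. The rule permits this but does not require it. If the drug lowers blood pressure, this route is likelier on active drug.
- *HD-associated symptoms (7.4.1.1).* Because 2.1.1 ties falls to chorea, an investigator could treat a fall as part of HD. It is then an event only if falls have increased. Judging an increase needs a reference, but the screening visit (8.1.1) asks for general medical history and HD history, not fall history. The HD symptom list in SAP 4.3.1 covers depression, behaviour and cognition. The definition of treatment-emergent worsening in 7.4.1.3 needs the same reference.
- *Elicitation.* No question asks about falls. Visits are up to three weeks apart, and 2.1.1 reports loss of recent memory among the cognitive changes seen in nearly all patients.

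**3. Size**

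The documents give no fall rate, so there is no planned figure to reproduce. The 43 per arm comes from the chorea endpoint. With a difference of 2.5, SD 3.5 and two-sided 0.025, a t-test with 39 per arm has 80.5% power, and 39 × 1.1 = 42.9, or 43. That calculation has no bearing on falls.

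For illustration, assume that 10% of placebo patients and 30% of patients on one dose fall, with n = 43 per arm and two-sided 0.05. With p̄ the mean of the two rates:

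power = Φ( [ |p1 − p0| − 1.96·√(2p̄(1 − p̄)/n) ] / √([p0(1 − p0) + p1(1 − p1)]/n) )

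- *Full recording, 10% vs 30%:* (0.200 − 1.96 × 0.0863) / 0.0835 = 0.37, so power is 64%. Difference 20 points, ratio 3.
- *Half missed in both arms, 5% vs 15%:* (0.100 − 1.96 × 0.0647) / 0.0638 = −0.42, so power is 34%. Difference 10 points, ratio still 3.
- *Half missed on active drug only, 10% vs 15%:* (0.050 − 1.96 × 0.0713) / 0.0711 = −1.26, so power is 10%. Difference 5 points, ratio 1.5.

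**4. Precision with complete recording**

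Power to detect a doubling at 43 per arm is 14%, 25%, 53% and 81% for placebo rates of 5%, 10%, 20% and 30%. At 10% vs 20%, the 95% CI half-width is 1.96 × √((0.09 + 0.16)/43) = 0.149, or about 15 points around a 10-point difference.

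**The case against.** A reader might infer that the rules file every fall under its injury or cause, and that the trial therefore cannot say whether the drug increases falls. The documents do not support this.

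- The unifying-diagnosis rule is generic and qualified. It mentions neither falls nor injuries, and a bruise or fracture is a consequence of a fall, not a diagnosis that unifies it.
- The HD exception names akathisia and dystonia, and it keeps symptoms that increase.
- SAP 4.10.1 counts every fall entered as a fall, by arm, with patients and events, in a randomised double-blind comparison.
- The SAP does not single falls out for omission, because 4.10.1 names no individual event.
- Related measures are planned: the incidence of orthostatic drops (SAP 4.10.2) and a gait sub-score that includes the pull test (SAP 4.7.2.5).

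All of this stands. It also stands that 2.1.6.1 and 2.2.1 introduce their lists as examples, that the synopsis is itself protocol text, and that no excess of falls over placebo is shown for the earlier trial. If the same share is missed in every arm, the ratio between arms is preserved. With 43 per arm, better recording alone would not settle the question.

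The objection does not remove the mismatch between the synopsis and the risk sections. Nor does it remove the two routes by which falls may be missed. Orthostatic drops and gait ratings are not counts of falls. Where falls are missed mainly on active drug, the ratio is not preserved.

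**Conclusion.** The concern holds as a risk of undercounting and as an inconsistency in the risk text. Falls are a named frequent event that three risk passages leave out. The recording rules allow some falls to be entered under another term or not at all, and no grouped falls summary is planned to recover them.

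The size of any undercount cannot be derived from the documents. The 10% and 30% rates and the one-half share are assumptions. Under them, the visible difference falls from 20 points to 10 if both arms lose equally, or to 5 if only the active arm does. That greater loss on active drug is plausible from the wording but is not shown. The descriptive comparison by arm remains, with low precision. This is a cheap improvement to the safety comparison, not a flaw that defeats it.

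**What to change.** 1. Reconcile protocol 2.1.6.1, 2.2.1 and 2.2.3 with the synopsis on falls.
2. Add to protocol 7.4.2.1: 'Every fall is recorded as its own adverse event, in addition to any injury or presumed cause, and whether or not it is attributed to HD.'
3. Add to SAP 4.10.1 one descriptive table by arm: patients with at least one fall, number of falls, and the difference of each dose from placebo with a 95% CI.
4. If recording can no longer be changed, specify before unblinding that falls for this table are identified from the verbatim terms. This recovers falls mentioned under another diagnosis, but not falls that were never entered.

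The cost is some protocol wording, a line of eCRF guidance and one table. The downside is a few more adverse event entries and slightly higher event totals in all arms.
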